## 6.5. Missing Data

For the primary endpoint of incidence of mechanical ventilation or death, subjects who are lost to follow-up before Day 29 prior to having an event and have their last assessment within window for Day 29 (i.e., Day 26, 27, 28) will be considered as non-events by Day 29 regardless of their discharge status at that time.

Remaining missing data for subjects lost to follow-up after discharge, while still hospitalized, or with no post baseline data will be imputed using multiple imputation. The main sensitivity analysis will consider subjects missing data while discharged as non-events and use a similar multiple imputation as the primary analysis for remaining missingness. Additional sensitivity analyses of the primary endpoint will use the same imputation approach as the primary analysis on different analysis populations and using different covariates in the final model.

Two secondary analyses of the primary endpoint will be conducted: the first is based on targeted maximum likelihood estimation (TMLE), and the second is a multiple imputation approach that uses TMLE for analysis of each imputed dataset. These approaches are described in Section 6.5.2.

Analysis of time to event endpoints (i.e., sustained recovery, time to improvement, time to mechanical ventilation or death) will be based on observed ordinal score along with discharge and death information. Refer to Table 2 for additional details regarding censoring and handling of missing data for all endpoints.

Some analyses of ordinal score such as ordinal scores over time described in Section 6.5.1 of the master SAP will be performed based on the complete dataset of ordinal score created using the following steps:

- All planned timepoints after death are assigned a score of 8
- Intermittent missingness:
  - Impute the intermittent missing ordinal score as 1 if the scores reported before and after the missing value are both 1 and no change in oxygen use or hospitalization status after discharge to a location other than hospice, long term acute care or other hospital.
  - Impute the intermittent missing ordinal score as 2 after discharge to a location other than hospice, long term acute care or other hospital if the subject doesn't fall into the category above and subject is not hospitalized at the time point.
  - Remaining intermittently missing data imputed using last observation carried forward.

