#### 6.5.1.2. Imputation Strategy for Subjects Lost to Follow-up while Discharged

This group includes subjects with post-baseline data available who were lost to follow-up or terminated early from the study prior to Day 29 and prior to death or progression to mechanical ventilation and were discharged to a location other than LTAC, hospice care or other hospital at the time of their last assessment.

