##### Imputation Approach if Less than 10 Events are Observed

If, as expected, less than 10 post-discharge events are observed in the discharged group, missing incidence of mechanical ventilation or death data for these subjects will be imputed from a simple binomial distribution with the event rate calculated as the proportion of discharged subjects with known outcome (i.e., discharged to a location other than LTAC, hospice care or other hospital) who died or progressed to mechanical ventilation after discharge, without adjusting for any covariates in this group.

If no event is observed in a given analysis such as in subgroup analyses, the event rate of 0.5/total number of discharged subjects with outcome in the subgroup will be used instead of 0.

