##### Pseudocode:

- DEFINE eventD29 as the binary variable for death or progression to mechanical ventilation or death by Day 29 (1=Yes, 0=No, .=Missing)
- DEFINE input2 as the analysis dataset containing discharged subjects with missing event.
- Define evnrate as the event rate among subjects discharged to a location other than LTAC, hospice care or other hospital who have known outcome.
- DEFINE imp\_out2 as the output dataset containing the 20 imputed datasets

```
data imp_out2;
  set input2;
  subid=input(substr(usubjid,5,4),best12.);
  seed=3849+subid;
  call streaminit(seed);
  p=&evnrate;
  do i=1 to 20;
    _imputation_ = i;
    eventD29=rand("Binomial",p,1);
    output;
  end;
  drop p i;
run;
```

imp\_out2 contains 20 imputed values for each subject discharged to a location other than LTAC, hospice care or other hospital who had missing event.

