### **Imputation Approach if 10 Events or More are Observed**

In the case that 10 post-discharge events or more are observed in this group of discharged subjects, missing events will be imputed using PROC MI adjusting for baseline ordinal score as shown in the below pseudocode.

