**Pe = Prob (Event by Day 29|no event through last assessment) = 1 – S29/SL**

**Step 4:** For each subject lost to follow-up while discharged or transferred to another hospital, impute the event from a binomial distribution using the event probability calculated in Step 3.

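### Subjects lost after a good discharge are imputed with the whole discharge-to-Day-29 event proportion whatever day they were last seen event-free, which is too high for later losses, with a small effect on the primary odds ratio

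*SAP*

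**What the plan says.** SAP 6.5.1 sorts subjects with a missing primary outcome into three groups and gives each its own imputation rule.

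- **Lost after a good discharge (6.5.1.2).** These subjects have post-baseline data, were "lost to follow-up or terminated early from the study prior to Day 29 and prior to death or progression to mechanical ventilation", and had gone to a location other than LTAC, hospice or another hospital. "If, as expected, less than 10 post-discharge events are observed in the discharged group", the outcome is "imputed from a simple binomial distribution with the event rate calculated as the proportion of discharged subjects with known outcome" who died or were ventilated after discharge, "without adjusting for any covariates in this group". The code passes the same constant for every subject and every imputation. The outcome runs through Day 29: "DEFINE eventD29 as the binary variable for death or progression to mechanical ventilation or death by Day 29".
- **The same group with 10 or more events.** Here "missing events will be imputed using PROC MI adjusting for baseline ordinal score". Day of last contact is again absent.
- **Lost while hospitalised or transferred (6.5.1.3).** The algorithm uses baseline covariates and the time of last assessment. Step 3 defines the probability as "Prob (Event by Day 29|no event through last assessment" and computes it as 1 − S29/SL.

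Before any of this, SAP 6.5 provides that subjects lost without an event who "have their last assessment within window for Day 29 (i.e., Day 26, 27, 28) will be considered as non-events by Day 29".

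The same imputation applies to key secondary 3 (SAP Table 2).

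**The concern.** The proportion used in 6.5.1.2 covers the whole period from discharge to Day 29. A subject lost after the Day 15 or Day 22 contact has already been seen event-free for part of that period and can have an unseen event only in the remainder. The relevant quantity is the probability of an event between last contact and Day 29, given none before. The plan uses that form for hospitalised losses but not for discharged ones.

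The Day 26–28 rule sharpens the inconsistency. A discharged subject last seen on Day 26 is a non-event. One last seen on Day 25, which is inside the Day 22 ± 3 visit window, gets the full discharge-to-Day-29 rate.

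The denominator has a related defect. Restricting it to known outcomes drops the event-free follow-up of the lost subjects, while every observed event stays in the numerator.

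At stake is the imputed event count in the primary analysis and key secondary 3. Too many imputed events in both arms, from a rate common to the arms, pull the odds ratio toward 1.

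**Working it through.** **1. The plan's own figure.** SAP Section 5 gives 80% power (control rate 16%) and 89% (21%) with 400 in the subgroup, odds ratio 2.5 and two-sided alpha 0.049. At 16%, the treated odds are (0.16/0.84)/2.5, so the treated rate is 7.08%; at 21% it is 9.61%. With 200 per arm, a two-proportion z-test gives 79.7% and 88.7%. Both agree with the SAP and are not in dispute.

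**2. Inputs.**

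- Post-discharge contacts on Days 8, 15, 22 and 29 (protocol 8.1.2.1).
- Imputation applies to last contacts up to Day 25 (SAP 6.5).
- Discharge timing: the only figure is about 75% discharged by Day 8, in the external LIVE-AIR subgroup (protocol 1.1.1). *Assumed here:* discharge on Day 7 or 8; range Day 5 to 15.
- Post-discharge hazard shape and event rate: not given. *Assumed:* constant hazard; range Weibull shape 0.5 to 1.5.
- *Assumed:* lost and followed subjects have the same hazard.

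**3. Overstatement factor.** For discharge day D and last contact L, the factor is [1 − S29/S(D)] / [1 − S29/S(L)]. With a low constant hazard this is close to (29 − D)/(29 − L).

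| Last contact | D = 7 | D = 8 |
|---|---|---|
| Day 8 | 22/21 = 1.05 | 21/21 = 1.0 |
| Day 15 | 22/14 = 1.6 | 21/14 = 1.5 |
| Day 22 | 22/7 = 3.1 | 21/7 = 3.0 |
| Day 25 | 22/4 = 5.5 | 21/4 = 5.2 |

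For a Day 22 loss:

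- Constant hazard: 2.0 (discharge Day 15) to 3.4 (discharge Day 5).
- Discharge Day 8: 2.2 (shape 1.5) to 5.4 (shape 0.5).
- All combinations tried: 1.5 to 6.3.
- A steeper decline, hazard halving every 7 days with discharge on Day 7, lies outside that range at 7.8.

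Against a rate pooled over an assumed mix of discharge days, a subject last seen on Day 4 is slightly *under*stated (factor 0.83 to 0.88).

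**4. Extra imputed events.** Assume 300 discharged subjects with known outcome, 4 to 8 post-discharge events, 20 discharged losses per arm, discharge on Day 7, and last contacts spread equally over Days 8, 15 and 22.

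- Constant hazard: the mean share of risk remaining is (21/22 + 14/22 + 7/22)/3 = 0.636. With 4 events the excess is (4/300) × 0.364 = 0.5 percentage points, or 20 × 0.005 = 0.1 events per arm.
- Hazard halving weekly: the mean share remaining is 0.468. With 8 events the excess is (8/300) × 0.532 = 1.4 points, or about 0.3 events per arm.

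**5. Effect on the odds ratio.** Expected events are 32 of 200 and 14.16 of 200, so the control-to-treated odds ratio is 2.50. Adding 0.3 to each arm gives (32.3/167.7)/(14.46/185.54) = 2.47, a shift of about 0.03.

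**6. A harsher case.** With 9 events in 300 and all losses at Day 22, the rule applies 3.0% where the conditional value is 1.0%. Twenty such losses per arm add 20 × 0.02 = 0.4 events, and the odds ratio becomes 2.46. Power falls from 79.7% to 79.4% if 5% of each arm is lost this way, and to 79.1% if 10% is.

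**The case against.** The strongest reply is that this hardly matters and that the plan already brackets it. Much of that stands. The SAP expects little missing data. Sensitivity analysis 1 and the second TMLE approach set discharged losses to non-events. The tipping-point analysis varies the missing event rate from 1% to 40% in each arm independently. Key secondary 1 censors at last assessment and so uses the event-free follow-up. What these do not supply is the conditional probability itself: for later losses the primary analysis is too high and Sensitivity analysis 1 is at zero.

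A second reply is that version 3.0 chose a simple proportion deliberately (SAP 15.2). That change concerned covariate adjustment when events are few. It does not address time last seen, and a single rate can respect it.

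A reader might infer several stronger points that the documents do not support:

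- *The rule adds events that the data exclude.* Observation excludes events only up to last contact; an imputed event can fall between then and Day 29. Only the probability is too high.
- *Three-fold is a property of the plan.* It comes from an assumed discharge day and hazard shape, neither of which is given for this trial.
- *Every discharged loss is overstated.* Losses near discharge are not.
- *The excess is equal in the two arms.* The rate is common, but equal excess also needs similar numbers and timing of losses, which the plan does not state.
- *Step 4 of 6.5.1.3 already covers home discharges*, because it and the definition of the dataset to be imputed speak of subjects lost while discharged or transferred. The section heading, its opening paragraph, Step 3 and the later dataset definition all say hospitalised or transferred, so this looks like a slip.

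**Conclusion.** The concern holds as a limited inconsistency. SAP 6.5.1.2 conditions on nothing that happened after discharge, whereas 6.5.1.3 and the Day 26–28 rule both take account of when the subject was last seen. For later losses the imputed probability is too high, provided that lost and followed subjects share one hazard. The Day 22 factor of about 3 is a central value under stated assumptions and should always be quoted with its range.

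The consequence is minor: a slight pull toward the null in the primary odds ratio and key secondary 3, with less than 1 point of power lost even if 10% of each arm were lost at Day 22. For the later losses at issue, the appropriate result lies between the primary analysis and Sensitivity analysis 1. The documents give no basis for expecting this step alone to change the trial's conclusion. It is worth correcting because it sits in the primary analysis and the correction is cheap.

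**What to change.** Impute each discharged loss conditionally on last contact, for example with

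Pe = 1 − exp(−λ × (29 − L)),

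where L is the study day of last contact and λ is post-discharge events divided by post-discharge person-days to Day 29. Lost subjects contribute person-days up to last contact, which also repairs the denominator. Keep the existing convention of 0.5 event when none is observed. As an illustration, 9 events over 300 × 21 = 6,300 person-days give λ = 0.00143, so Pe is 2.0% for a Day 15 loss and 1.0% for Day 22, in place of 3.0% for both.

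With 10 or more events, use the same conditional form from a time-to-event model with baseline ordinal score.

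A rate is preferable to a Kaplan-Meier curve here. With 4 events and discharge on Day 7, the chance that none falls after Day 22 is (15/22)^4 = 22% at constant hazard and about 58% if the hazard halves weekly. The curve would then impute exactly zero for a Day 22 loss, and the 0.5-event convention would not apply.

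In the same edit, reconcile the discharged-or-transferred wording in the 6.5.1.3 pseudocode and Step 4 with that section's heading.

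The cost is a paragraph of SAP text, a short program change, and an assumption of constant hazard after discharge in the branch with fewer than 10 events.

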##### Pseudocode:

- DEFINE eventD29 as the binary variable for death or progression to mechanical ventilation or death by Day 29 (1=Yes, 0=No, .=Missing)
- DEFINE input2 as the analysis dataset containing discharged subjects with missing event.
- Define evnrate as the event rate among subjects discharged to a location other than LTAC, hospice care or other hospital who have known outcome.
- DEFINE imp\_out2 as the output dataset containing the 20 imputed datasets

```
data imp_out2;
  set input2;
  subid=input(substr(usubjid,5,4),best12.);
  seed=3849+subid;
  call streaminit(seed);
  p=&evnrate;
  do i=1 to 20;
    _imputation_ = i;
    eventD29=rand("Binomial",p,1);
    output;
  end;
  drop p i;
run;
```

imp\_out2 contains 20 imputed values for each subject discharged to a location other than LTAC, hospice care or other hospital who had missing event.

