#### **Pseudocode:**

- DEFINE input2 as the analysis dataset containing all discharged subjects including those with missing event to be imputed and those with known outcome.

```
proc mi data=input2 out= imp_out2 n impute=20 seed = 748485 noint;
class baseordscorevar eventD29;
var eventD29;
monotone logistic(eventD29= baseordscorevar);
run;
```

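### SAP 6.5.1.2, branch for 10 or more post-discharge events: the imputation model counts ventilations that happened before discharge

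*SAP*

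**What the plan says.** SAP 6.5.1.2 covers subjects with post-baseline data who were lost "prior to Day 29 and prior to death or progression to mechanical ventilation and were discharged to a location other than LTAC", hospice care or another hospital. Everyone imputed here was therefore event-free when last seen. The section has two branches.

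- **Fewer than 10 post-discharge events (the expected case).** Missing outcomes are drawn from a binomial distribution "with the event rate calculated as the proportion of discharged subjects with known outcome" (to an eligible location) "who died or progressed to mechanical ventilation after discharge, without adjusting for any covariates in this group". The pseudocode then has three definitions: "DEFINE eventD29 as the binary variable for death or progression to mechanical ventilation or death by Day 29"; "DEFINE input2 as the analysis dataset containing discharged subjects with missing event"; and "Define evnrate as the event rate among subjects discharged to a location other than LTAC, hospice care or other hospital who have known outcome". If no event is observed, a rate of 0.5 divided by the number of discharged subjects with outcome is used.
- **Ten or more.** The trigger reads: "In the case that 10 post-discharge events or more are observed in this group of discharged subjects". The dataset changes: "DEFINE input2 as the analysis dataset containing all discharged subjects including those with missing event to be imputed and those with known outcome". PROC MI then fits a monotone logistic model to that dataset, with `eventD29` as the response and baseline ordinal score as the only predictor.

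SAP 15.2 also describes the threshold as counting events after discharge.

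**The concern.** The fallback branch is chosen by counting one event and then models another. It is triggered by events after discharge, but its response is any event by Day 29, and no line removes or recodes subjects whose event came before discharge. Take a subject ventilated on Day 4, extubated, and discharged home on Day 24. That subject is discharged, has a known outcome and has `eventD29` = 1, so the model treats the case as evidence of risk after discharge although nothing happened after discharge. The subjects being imputed have already passed the in-hospital period without an event.

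SAP 6.5.1.3 handles the parallel group, those lost while hospitalized or transferred, correctly: it conditions on no event through the last assessment.

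The step feeds the primary analysis, the sensitivity analyses that reuse the primary imputation, and key secondary endpoint 3. For subjects with baseline score 7 in that secondary analysis, only death counts, so earlier ventilation cannot raise their rate.

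**Working it through.** **1. The plan's own figure.** SAP 5 states 80% and 89% power for 400 subjects, odds ratio 2.5 and two-sided alpha 0.049. I take 200 per arm.

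- Control 16%: treated odds = (0.16/0.84)/2.5 = 0.0762, so the treated rate is 7.08%. The pooled SE is 0.03195 and the unpooled SE 0.03164. Power = Φ[(0.0892 − 1.969 × 0.03195)/0.03164] = 79.7%.
- Control 21%: the treated rate is 9.61% and power is 88.7%.

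Both figures reproduce and neither is affected by this point. They supply the expected event count: 200 × (0.16 + 0.0708) = 46.2 events, of which 32 are on placebo and 14.16 on lenzilumab.

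**2. Assumptions.** The documents give no post-discharge counts. I vary:

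- k, the number of post-discharge events: 10, 12 or 15;
- f, the share of the other events that are ventilated survivors discharged with known outcome: 10%, 25% or 40%;
- the number of discharged subjects with missing outcome: 8 to 20 in total (2–5% of 400).

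All non-events are treated as discharged with known outcome.

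**3. Fallback branch.** Let h = f × (46.2 − k). Donors event-free at discharge number n0 = 400 − 46.2 + k. All discharged donors number n1 = n0 + h.

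- Rate needed: k/n0.
- Post-discharge rate among all discharged: k/n1.
- Rate as coded: (k + h)/n1.

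| k | f | h | k/n0 | k/n1 | As coded | Coded ÷ (k/n1) |
|---|---|---|---|---|---|---|
| 10 | 10% | 3.6 | 2.75% | 2.72% | 3.71% | 1.36 |
| 10 | 40% | 14.5 | 2.75% | 2.64% | 6.47% | 2.45 |
| 12 | 25% | 8.5 | 3.28% | 3.21% | 5.49% | 1.71 |
| 15 | 10% | 3.1 | 4.07% | 4.03% | 4.87% | 1.21 |
| 15 | 40% | 12.5 | 4.07% | 3.93% | 7.20% | 1.83 |

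The ratio runs from 1.2 to 2.5. Measured against k/n0 instead, it runs from 1.2 to 2.4. Extra imputed events over both arms = missing subjects × (coded − k/n1). The smallest value is 8 × (4.87% − 4.03%) = 0.07 and the largest is 20 × (6.47% − 2.64%) = 0.77.

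**4. Effect on the odds ratio (placebo : lenzilumab), worst row.** Add (losses × rate) to 32 and 14.16 events, with 200 per arm, and compare 2.75% with 6.47%.

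- 10 losses per arm: at 2.75%, (32.275/167.725)/(14.434/185.566) = 2.47; at 6.47%, 2.44.
- 20 placebo and 5 lenzilumab losses: 2.52 becomes 2.56.

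The first shift is ln(2.474/2.440) = 0.014. The standard error of the log odds ratio is about √(1/32 + 1/168 + 1/14.16 + 1/185.84) = 0.34, so the shift is about 4% of one standard error.

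**5. Expected branch.** The text's numerator is post-discharge events only, so no inflation arises. Its denominator keeps subjects already ventilated, who can no longer have a first event. With k = 5, the rate is 1.33–1.38% against 5/358.8 = 1.39% among those event-free at discharge: slightly low, not high.

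**The case against.** **A stronger reading is tempting but not supported.** Because `evnrate` is worded without the after-discharge limit, just below the definition of `eventD29`, a reader might infer that the expected branch is inflated too. The documents do not say so. The governing sentence under the same sub-heading limits the numerator to events after discharge. The code never names `eventD29` as the numerator of `evnrate`. The `input2` dataset there holds only subjects with a missing outcome, so `eventD29` is the variable being filled in. This is an abbreviation to tidy, not a second error.

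**A reader might also infer that the bias always runs toward 1.** Treatment is not in this imputation model, so when losses are similar by arm the excess does pull toward 1. With unequal losses it need not, as the 20-and-5 example shows.

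**The fallback branch may never be used.** Ten post-discharge events would be 10/46.2 = 22% of all expected events, the SAP expects fewer than 10, and it expects little missing data. That is fair and limits the severity.

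**Other analyses bound the effect.** The main sensitivity analysis and the second TMLE approach set discharged subjects with missing outcome to non-events. The first TMLE approach does not use this step. The tipping point analysis sets its own rates. All of this stands, but none of it corrects the primary estimate if the branch is triggered.

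**It might be said that the section's opening already confines donors to event-free subjects.** That sentence describes who is lost and imputed. The fallback dataset is expressly defined as all discharged subjects, including those with known outcome.

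**Conclusion.** The point holds for the branch with 10 or more post-discharge events: as written, its response variable and donor set do not match the risk being imputed. Under the assumed ranges the probability is about 1.2 to 2.5 times too high, which means about 0.1 to 0.8 extra imputed events for 8 to 20 missing subjects and a change of a few hundredths in the odds ratio. The direction is toward 1 when losses are similar by arm and can be either way otherwise. These sizes rest on assumed shares and loss counts; the mismatch itself is on the face of the SAP.

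In the expected branch the numerator is right, the code wording is loose, and the denominator is slightly too large. The main sensitivity analysis and the second TMLE approach are unaffected. Whether subgroup rows are affected cannot be settled, because SAP Table 2 applies the primary imputation to them while footnote h of Table 4 says they run without it. Severity: minor.

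**What to change.** In SAP 6.5.1.2:

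1. Define a separate indicator: first invasive ventilation/ECMO or death after discharge to an eligible location and by Day 29.
2. In the branch for 10 or more events, restrict `input2` to subjects event-free at discharge and use the new indicator, not `eventD29`, as the response. Carry the imputed value into `eventD29` afterwards.
3. In the branch for fewer than 10 events, restrict the denominator to subjects event-free at discharge, and do the same for the 0.5/total rule.
4. Repeat the after-discharge limit in the `evnrate` definition.

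While editing the fallback code, note that its VAR statement lists only `eventD29` although the model also uses `baseordscorevar`.

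The cost is a few lines of wording and code, with no new data. The SAP already needs discharge timing and location and event timing to count post-discharge events.
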